6 STATISTICAL CONSIDERATIONS

This study will evaluate the effectiveness and safety of the ExAblate 2100 Prostate System for the treatment of patients with intermediate-risk, localized prostate lesions. All patients will be consented and followed as it would be defined by 510k submission/approval requirements. Data will be analyzed for efficacy based on data collected per FDA agreement for a 510(k) commercial clearance as previously discussed with FDA. Patients will continue to be followed post treatment for long-term outcomes.

6.1 Sample Size

The current IDE has had 4 amendments to date. The 4th Amendment aim was to define the patient population that will be part of the 510K submission (IDE G100108/S011). To ensure a cohesive patient population for the 510K FDA review, only those patients treated after site IRB approval of Amendment 4 will be counted toward the primary analysis population. Other safety and efficacy analyses that include data from subjects enrolled prior to the approval of G100108/S011 may be reported as supplementary information.

To date (Sept-20-2018), 81 patients have been treated under protocol Amendment-4.

Based on our accumulated experience when conducting studies for a new indication, there is a great level of experience and knowledge acquired from a study in which many sites participate in the study. This has proven to be critical in the design and conduct of Pivotal studies. The need for at least 15 sites in the proposed study is further supported by the discussion of the FDA panel meeting discussing prostate focal therapy, and also by the Pivotal study that is running for the Sonablate 500 ultrasound HIFU device for a population that is similar to the proposed study.

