Consented and enrolled patients will be assessed for eligibility by undergoing 14 core or more mapping biopsy will use a standard template (such as described in Appendix C, as an example) by either transperineal or transrectal access where 2 of these biopsies are directed anteriorly on the right and left hemigland. Biopsy tissue specimens at screening and post-treatment will be processed and analyzed locally at each clinical site, for determining study eligibility and individual patient care throughout the study. Patients with positive pre-treatment biopsies and correlating multi-parametric MR findings meeting all other inclusion and exclusion criteria may be enrolled into the study.

This proposed study will be a prospective, single arm study of a minimum of 100 and a maximum of 103 patients treated at up to 15 sites.

Study will be performed utilizing either 1.5T or 3T MR scanners with a torso P/A or cardiac P/A coil. MR imaging at screening may include an endorectal coil.

Follow-up will focus on device- or procedure-related adverse events for primary safety analysis. Efficacy will be based on outcomes of mapping biopsy outcome at the 6 month follow-up period or sooner per future discussion(s) with the FDA for the 510K submission.

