6.2 Data Analysis

6.2.1 510(k) Analysis

This is a clinical study involving a minimum of 100 to a maximum of 103 subjects. Descriptive analyses of safety and effectiveness data will be used to summarize results for a 510(k) submission for commercial clearance. Safety and effectiveness data will address both results of biopsy as well as functional analysis.

Primary effectiveness analyses will be based on the 6-month biopsy results. Proportions of treated patients reporting a negative biopsy and/or MRI verification of index lesion ablation at 6-months.

Descriptive summaries will be presented for: PSA testing, NRS, FACT-P (v4), IPSS, and SF-12 questionnaires and percentage of non-perfused volume (NPV).

Baseline assessment of erectile dysfunction and incontinence will be captured as per the incontinence/ED questionnaires and they will be followed also using the same questionnaires. Any

Focal MR-Guided Focused Ultrasound Surgery of Intermediate risk, Localized Prostate Lesions

worsening of the baseline condition to a worsened CTCAE grade will be captured as an adverse event and will be graded on CTCAE Version 4.0 published May 28, 2009 (v.4.03:June 14, 2010) and will be reviewed by the Data Safety Monitoring Board.

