7.1.8 Anticipated MRgFUS Treatment Side Effects

Based on previous treatment experience, the above listed side effects have been identified as possible treatment-related complications of ExAblate treatment and procedure. These can be classified into Non-significant and Significant Anticipated Treatment Side Effects based on their medical severity, additional treatment required and long term consequences for the patient. All Treatment Side Effects will be reported in the Case Report Forms for the study and included in the final study analysis.

Non-significant Anticipated Treatment Side Effects of ExAblate treatments are those, which normally resolve without sequelae within 10-14 days of the treatment.

Significant Anticipated Treatment Side Effects of ExAblate are those which may require medical treatment, may have sequelae, and for which time of resolution is not defined. The

Focal MR-Guided Focused Ultrasound Surgery of Intermediate risk, Localized Prostate Lesions

rate of anticipated significant treatment side effects of the ExAblate treatment is unknown, but expected to be infrequent based on prior clinical experience in other organs.

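### Safety reporting for men treated before Amendment 4 is optional in 2.1.2 and 6.1, which conflicts with 7.1.8, and the two sentences that define the groups use different cut points

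*Combined protocol and SAP*

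**What the plan says.** Section 6.1, repeated in 2.1.2, sets the primary population: "only those patients treated after site IRB approval of Amendment 4 will be counted toward the primary analysis population". The reason given is "To ensure a cohesive patient population for the 510K FDA review". The next sentence deals with everyone else: "Other safety and efficacy analyses that include data from subjects enrolled prior to the approval of G100108/S011 may be reported as supplementary information". It names safety as well as efficacy, and its verb is permissive.

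Section 6.2.1 describes the 510(k) analysis: "Descriptive analyses of safety and effectiveness data will be used to summarize results for a 510(k) submission for commercial clearance". It names no safety population. Section 6.2.2 refers the final analysis back to the 510(k) requirements and names none either.

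Other sections carry no amendment limit. Section 7.1.8 says: "All Treatment Side Effects will be reported in the Case Report Forms for the study and included in the final study analysis". Section 2.2 states the safety objective as the incidence and severity of device- or treatment-related complications up to 24 months. Section 7.4 has investigators document related events and report every serious event to the sponsor and IRB. Section 7.5 has safety monitoring review all adverse events.

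On progress, 6.1 states: "To date (Sept-20-2018), 81 patients have been treated under protocol Amendment-4". The target in 6.2.1 is: "This is a clinical study involving a minimum of 100 to a maximum of 103 subjects".

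**The concern.** A common cohort for the main effectiveness result is reasonable. The difficulty is that the same cut carries over to safety. Under the rule in 2.1.2 and 6.1, the sponsor could submit a safety table that leaves out men treated with the same device under the same IDE, and could decide whether to show them at a time when their outcomes can be known. No section defines an all-treated safety set or requires a table for the earlier men.

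Safety is a stated objective, and the study is small for uncommon harms. A reader of the 510(k) tables could not tell whether the earlier men were left out because the plan required it or because someone chose to. Fixing the rule in advance removes that question whatever their results were.

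**Working it through.** **1. The plan's own figure.** The 100 to 103 subjects cannot be reproduced. Section 6.1 gives no rate, error level or power, and 6.2.1 calls the analysis descriptive. The check is therefore of the text, followed by an illustration.

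**2. The conflicting sections side by side.**

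| Section | Men covered | Commitment |
|---|---|---|
| 2.1.2 and 6.1, first sentence | After site IRB approval of Amendment 4 | Primary population |
| 2.1.2 and 6.1, second sentence | Analyses that include earlier subjects | Optional |
| 7.1.8 | No amendment limit | All side effects in the final analysis |
| 2.2 | No amendment limit | Incidence and severity to be evaluated |
| 7.4, 7.5 | No amendment limit | Collection, notification, review |
| 6.2.2 | Not named | As the 510(k) requires |

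An optional report and a promise to include everything cannot both govern the same men. Sections 7.4 and 7.5 do not settle it, because collection and review are not a commitment to tabulate. Section 6.2.2 does not settle it, because Amendment 4 is what defined the 510(k) population.

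**3. The cut points.** The first sentence sorts by date of treatment against approval at the site's IRB. The second sorts by date of enrolment against approval of supplement S011.

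| | Treated before site IRB approval | Treated after site IRB approval |
|---|---|---|
| Enrolled before S011 approval | Optional supplement | Primary **and** optional supplement |
| Enrolled after S011 approval | **Neither** | Primary |

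A man in the lower left cell is not covered even by the optional sentence. The documents do not say whether any man falls in the lower left or upper right cell.

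**4. Timing.** 81/100 = 81% and 81/103 = 79% of the primary cohort had been treated when this version was written, leaving 19 to 22. The design is single arm (2.1: "single arm study of a minimum of 100 and a maximum of 103 patients treated at up to 15 sites") and no masking is described.

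**5. What 100 to 103 men can show.** Section 7.1.7 gives about 0.5% for fistula with ultrasound-guided HIFU. At that rate the chance of at least one event is 1 − 0.995^n, which is 39% for n = 100 and 40% for n = 103. For harms of that order, each treated man adds usable information.

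**6. Illustration of size.** The number of earlier men, m, is not given; m = 5 to 40 is assumed. Take no events in 100 primary men. Exact two-sided 95% upper limits are 1 − 0.025^(1/n) for zero events, and the p that solves (1 − p)^n + n·p·(1 − p)^(n−1) = 0.025 for one event.

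| m | Share of all treated, m/(100 + m) | No event in earlier men: upper limit | One event in earlier men: rate, upper limit |
|---|---|---|---|
| 5 | 4.8% | 0/105: 3.5% | 1/105 = 1.0%, 5.2% |
| 20 | 16.7% | 0/120: 3.0% | 1/120 = 0.8%, 4.6% |
| 40 | 28.6% | 0/140: 2.6% | 1/140 = 0.7%, 3.9% |

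The primary-only figure is 0/100, upper limit 3.6%. Adding the earlier men can tighten or widen the bound, depending on what happened to them.

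**The case against.** The strongest reply is that the cut has a stated, neutral reason. It is tied to a numbered IDE supplement and to IRB approval, and nothing suggests that outcomes drove it. The reason is not limited to effectiveness. Harms are not hidden: serious events go to the sponsor and IRB, safety monitoring reviews all events, and 7.1.8 can be read together with a permissive sentence about supplementary analyses. Eligibility and event grading under earlier amendments are not in the documents, so the groups may not be comparable.

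Much of this stands. It supports a separate primary cohort and separate display of the periods. It does not explain why safety reporting in the earlier men should be optional, and it leaves the conflict with 7.1.8 unresolved.

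A reader might also infer more than the documents support:

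- **That each site's first cases are dropped.** This is true only of sites that treated men before their own IRB approved Amendment 4. A site that joined later has its first cases in the primary set, and the mix of sites is not given.
- **That 6.1 concedes an operator learning curve.** Its remarks on experience argue for using many sites. They do not say that early outcomes were worse.
- **That the main safety rates are biased downward.** That would require higher rates in the earlier men, which the documents neither show nor exclude.
- **That all the harms at issue are rare.** Section 7.1.4 gives urethral or bladder neck stricture as 1 to 25%, so zero-event limits are not a general guide.

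**Conclusion.** The point holds as a reporting defect that should be corrected before analysis. Sections 2.1.2 and 6.1 make safety reporting for men treated before Amendment 4 optional, 7.1.8 promises that all side effects enter the final analysis, and the choice is not fixed before results can be known. The mismatched cut points are a second, smaller fault in the same two sentences.

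The real size cannot be stated without the number of earlier men and their events. The figures above are illustrations that rest on assumed values of m and assumed event counts. The finding does not depend on them, because it follows from the text. It does not imply that harms were concealed, that the exclusion was chosen because of harms, or that the reported rates will be too low.

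**What to change.** Keep the Amendment 4 cut for primary effectiveness. In both 2.1.2 and 6.1:

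1. Define the earlier and later groups by one cut point, used in both sentences, so that every treated man falls in exactly one group.
2. For safety, replace the permissive wording with: *Adverse events will be reported for all men who received at least one sonication under G100108 under any amendment, including men later classed as screen failures after sonication, shown by amendment period beside the post-Amendment 4 set.*
3. Name this set in 6.2.1 and 6.2.2, so that they agree with 7.1.8.

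The words on screen failures are needed because 4.3, step 23, allows a man to be reclassified and exited after the first three therapeutic sonications.

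The cost is a few sentences and one more set of adverse event tables, from events the protocol already requires to be recorded. The safety rates may turn out less favourable. Eligibility and event grading may have differed under earlier amendments, which is why the periods are shown separately and not only pooled.

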6.2 Data Analysis

6.2.1 510(k) Analysis

This is a clinical study involving a minimum of 100 to a maximum of 103 subjects. Descriptive analyses of safety and effectiveness data will be used to summarize results for a 510(k) submission for commercial clearance. Safety and effectiveness data will address both results of biopsy as well as functional analysis.

Primary effectiveness analyses will be based on the 6-month biopsy results. Proportions of treated patients reporting a negative biopsy and/or MRI verification of index lesion ablation at 6-months.

Descriptive summaries will be presented for: PSA testing, NRS, FACT-P (v4), IPSS, and SF-12 questionnaires and percentage of non-perfused volume (NPV).

Baseline assessment of erectile dysfunction and incontinence will be captured as per the incontinence/ED questionnaires and they will be followed also using the same questionnaires. Any

Focal MR-Guided Focused Ultrasound Surgery of Intermediate risk, Localized Prostate Lesions

worsening of the baseline condition to a worsened CTCAE grade will be captured as an adverse event and will be graded on CTCAE Version 4.0 published May 28, 2009 (v.4.03:June 14, 2010) and will be reviewed by the Data Safety Monitoring Board.

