2 OBJECTIVES

2.1 Background

Objective of this trial is to assess safety and effectiveness of ExAblate MRgFUS in the treatment of intermediate risk, localized (organ confined) prostate lesions. Investigators selected for the study will be trained on proper use of the ExAblate system (**Appendix B**).

ExAblate treatment will be implemented as a focal lesion-selective therapy, directed at pre-defined volume(s)/sector(s) in the prostate, identified abnormal by mapping biopsy and multi-parametric MRI), rather than a whole gland or hemi-ablation treatment.

Safety: evaluate incidence and severity of adverse events associated with ExAblate's MRgFUS focal treatment of intermediate risk organ confined prostate lesions. The risk of ExAblate treatment-related incontinence and impotence will also be assessed in this study.

Focal MR-Guided Focused Ultrasound Surgery of Intermediate risk, Localized Prostate Lesions

Effectiveness: determine the lesion control effect of ExAblate's MRgFUS focal treatment of intermediate risk organ-confined prostate lesion (confirmed by IMAGE-guided mapping biopsy results).

The proposed study is to evaluate the preliminary effectiveness and safety of the ExAblate 2100 Prostate System for focal treatment of patients with intermediate risk, localized prostate lesions. Study results will be submitted to FDA as previous discussions with the Agency in a 510k for commercial clearance.

Per FDA requirement, the full 510K submission will be performed following the last treated subject completing their 12-Months visit. Assessments of primary efficacy endpoints will compare the 6-months after ExAblate treatment to Baseline measurements. Safety of ExAblate Prostate treatment will be collected for one year after ExAblate.

It should be noted that all patients will be consented and followed up all the way to 24-Months post treatment.

This study will allow any IMAGE-guided biopsy methodologies (transrectal or transperineal) of 14 cores or more to be used for baseline lesion localization and characterization and for follow-up, but the methodology used should be consistent at all time points for each subject. Successful lesion ablation by ExAblate would result in no residual and/or recurrent lesion at the 6 or 24 month follow-ups. Additional biopsies may be performed between 6- month follow-up visits if judged to be clinically indicated by the investigator.

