2.3 Effectiveness

Results of prostate mapping biopsies will be used to assess lesion control achieved by the treatment.

Focal MR-Guided Focused Ultrasound Surgery of Intermediate risk, Localized Prostate Lesions

Post-treatment PSA, non-perfused volume (NPV), FACT-P (Version 4), ICIQ-SF, IPSS, IIEF-15 and SF12 questionnaire results through Month 24 visit will be summarized as secondary measures of effectiveness.

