2.3.1 Central Pathology Assessment

To assist in evaluating effects of ExAblate focal therapy for prostate lesion, this study is utilizing a central pathology lab to standardize interpretation of post-treatment effects. If Gleason graded tumor is identified in the 6 month biopsy in the treatment zone of the specimen, then it will be sent to a central pathology lab for confirmation and grading. If a discrepancy is reported between the site and the lab, then the judgment of the central pathology lab will take precedence. Decisions about patient eligibility and post-treatment care will be determined by the local site principal investigator, based upon results of the site pathological findings and clinical examination.

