- 21.** Actual treatment will begin. Per each slice, planning software will compute the treatment plan with the beam path delineated. Treating physician will review/edit the sonications and make modifications as needed. Sonications will be performed according to plan.
- 22.** Effect of each sonication will be measured by MR thermometry. Acoustic power will be adjusted throughout the treatment, to achieve temperatures between 65°C and 85°C at focal point.
- 23.** Sonications will continue until entire target volume has been treated. The goal is a total procedure (i.e. ablation or sonication) time of up to 180 minutes. If the doctor determines the planned treatment is not possible after the first 3 therapeutic sonications, and another treatment session is not planned, the patient will be considered a screen failure and exited from the study. The reason for early exit will be documented on the CRF. The patient will be taken to recovery area for observation and release. The patient will undergo a 1-week follow-up visit for safety purposes, prior to study exit.
- 24.** After completion of the treatment, a final MR scan will be done. This scan will include T2 weighted and T1 contrast enhanced sequences including subtraction to evaluate tissue ablation.
- 25.** Transrectal device will be removed by physician and then patient will be transferred from the magnet/ ExAblate Suite to a recovery room for an observation period, according to clinical considerations.
- 26.** Treatment exports and all MR images taken during the study will be archived by the Sponsor.
- 27.** In the event of an incomplete treatment due to device failure, patient request, physician's decision, or unforeseen circumstance, a second treatment will be offered to the patient, provided no medical contraindications exist. Second treatment will be scheduled within 12 weeks from the original treatment. Patient follow-up visits will be based on the date of the second treatment.
- 28.** Patient should complete a post-treatment NRS.

Focal MR-Guided Focused Ultrasound Surgery of Intermediate risk, Localized Prostate Lesions

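### Section 6.2.1 rests primary effectiveness on the 6-month biopsy but words the proportion as biopsy 'and/or' MRI, so read literally MRI alone can make a biopsy-positive man a success

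*Combined protocol and SAP*

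**What the plan says.** Section 6.2.1 has two adjacent sentences on primary effectiveness. The first is "Primary effectiveness analyses will be based on the 6-month biopsy results". The second, a fragment without a verb and the only wording of the proportion, is "Proportions of treated patients reporting a negative biopsy and/or MRI verification of index lesion ablation at 6-months".

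Elsewhere efficacy rests on biopsy. Section 2.1 (study design text) says "Efficacy will be based on outcomes of mapping biopsy outcome at the 6 month follow-up period or sooner per future discussion(s) with the FDA". Section 2.3 says "Results of prostate mapping biopsies will be used to assess lesion control achieved by the treatment" and then lists non-perfused volume, an imaging measure, among the secondary measures.

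Three other provisions bear on the count:

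- Section 4.4 (item 6d) and the Section 5 schedule give every patient both a mapping biopsy and a multi-parametric MRI at 6 months.
- Section 2.3.1 governs central pathology. Tumour found at the site "in the treatment zone of the specimen, then it will be sent to a central pathology lab for confirmation and grading", and "If a discrepancy is reported between the site and the lab, then the judgment of the central pathology lab will take precedence".
- Section 4.3 (item 23) covers men in whom the planned treatment proves impossible: "after the first 3 therapeutic sonications, and another treatment session is not planned, the patient will be considered a screen failure and exited". They have a 1-week safety visit and leave, so they have no 6-month biopsy.

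**The concern.** The two sentences of Section 6.2.1 do not describe the same endpoint. The first makes biopsy the basis. The second, read literally, gives MRI equal standing as a route to success. A man whose 6-month biopsy still shows cancer could then be scored a success because MRI was read as showing the index lesion ablated.

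The fragment supports at least four readings: biopsy or MRI, biopsy and MRI, biopsy alone with MRI mentioned loosely, or two rates side by side. The only precedence rule in the documents is central over site pathology. It does not cover disagreement between biopsy and MRI.

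This is a single-arm study with a descriptive analysis, so this proportion is the main effectiveness result offered for the 510(k). If its numerator can be settled after the results are known, a reader cannot tell what it measures.

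**Working it through.** **No figure to reproduce.** The plan gives no expected success rate, performance goal, alpha or power. The check is therefore logical, followed by an illustration in which every rate is assumed.

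**Step 1: how each reading scores a man** (missing biopsy counted as failure under biopsy only).

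| 6-month biopsy | MRI verifies ablation | Biopsy only | 'Or' | 'And' |
|---|---|---|---|---|
| Negative | Yes | success | success | success |
| Negative | No | success | success | failure |
| Positive | Yes | failure | **success** | failure |
| Positive | No | failure | failure | failure |
| Missing | Yes | failure | **success** | failure |
| Missing | No, or not done | failure | failure | failure |

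**Step 2: direction.** Let b be the share of treated men with a negative biopsy, m the share MRI-verified, and a the share with both.

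- 'And' rate = a, which lies between max(0, b + m − 1) and min(b, m), so it is never above b.
- 'Or' rate = b + m − a, which lies between max(b, m) and min(1, b + m), so it is never below b.

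This holds whatever the rates are.

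**Step 3: illustration.** Assume N = 100 (the plan has 100 to 103), 80 negative, 20 positive and none missing, with MRI verifying 90% of the negatives (72 men) and 50% of the positives (10 men). Intervals are exact 95%.

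- 'And': 72/100 = 72% (62.1 to 80.5)
- Biopsy only: 80/100 = 80% (70.8 to 87.3)
- 'Or': (80 + 10)/100 = 90% (82.4 to 95.1)

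Check: m = (72 + 10)/100 = 0.82, and b + m − a = 0.80 + 0.82 − 0.72 = 0.90.

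**Step 4: how far the gap depends on the assumptions.** The excess of 'or' over biopsy only is v × (positives + missing men who have an MRI)/N, where v is the share of those men whom MRI verifies.

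- v = 0: no excess.
- v = 0.3 with 10 positive: 3 points.
- v = 0.9 with 40 positive: 36 points.
- v = 0.9 with 36 positive and 10 missing who all have an MRI: 0.9 × 46 = 41.4, about 41 points.

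The last case is strained: biopsy and MRI belong to the same visit, so a man who misses one may well miss the other.

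**Step 5: missing biopsies.** Assume 72 negative, 18 positive, 10 missing and v = 0.5.

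- Biopsy only, missing as failure: 72/100 = 72%.
- Biopsied men only: 72/90 = 80%.
- 'Or', if the ten have no MRI: (72 + 9)/100 = 81%.
- 'Or', if all ten have an MRI: (72 + 14)/100 = 86%.

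**Step 6: two smaller choices in the same proportion.** Both start from 80 negative of 100.

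- If 1, 3 or 5 of the other 20 are early exits under Section 4.3, leaving them out gives 80/99 = 80.8%, 80/97 = 82.5% or 80/95 = 84.2%.
- Only site-positive treatment-zone specimens go to central review, so review can turn a positive into a negative but never the reverse. If all 20 positives are in the zone and 'negative' means the zone, overturning 1, 3 or 5 gives 81%, 83% or 85%. Under a whole-gland definition an overturned zone reading need not create a success.

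**The case against.** The best defence is that biopsy was plainly meant. The preceding sentence says so, Sections 2.1 and 2.3 agree, and both Section 2.3 and Section 6.2.1 keep non-perfused volume apart from the primary measure. The plural opening of the fragment fits two rates reported side by side. Both tests are scheduled for everyone, so every version can be shown. The analysis is descriptive with no threshold, and Section 6 refers to an agreement with FDA that may fix the definition.

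Most of this stands, and it limits the point. Several stronger readings are tempting, but the documents do not support them:

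- A reader might infer that the sponsor means MRI to override a positive biopsy. The surrounding text points the other way; this is contradictory wording, not evidence of intent.
- A reader might infer that imaging is nowhere ranked below biopsy. Section 2.3 does rank one imaging measure as secondary. What is missing is a rule for the 6-month MRI verification named in the fragment.
- A reader might cite the Section 2.1 objective, "organ-confined prostate lesion (confirmed by IMAGE-guided mapping biopsy results", as a further statement of a biopsy endpoint. The parenthesis may only describe how the lesion was confirmed at baseline, so I do not rely on it.
- A reader might say the early exits are unclassified. Section 4.3 labels them screen failures, which in ordinary usage puts them outside the analysis. The plan does not say so for this proportion, although they have received therapeutic sonications.
- A reader might take 10, 36 or 41 points as the expected inflation. Those figures follow from assumed rates.

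The defence does not remove the conflict between two adjacent sentences. An agreement whose terms are not in the plan cannot resolve it for a reader of the plan.

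**Conclusion.** The concern holds as an internal contradiction in the only sentence that words the primary proportion. Read literally, it allows success on MRI alone for a man with a positive 6-month biopsy, or for one with no biopsy who has an MRI. No passage settles disagreement between biopsy and MRI or the scoring of a missing biopsy.

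The direction is certain once missing is counted as failure: 'or' is at or above biopsy only, and 'and' is at or below it. The size is unknown and could be zero if MRI never verifies ablation in a man without a negative biopsy.

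A reader might infer an effect on type I error, power or a success decision. There is none, because the plan has no test or threshold. What changes is the value and meaning of the headline proportion for the 510(k). This should be fixed, but it does not invalidate the study.

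**What to change.** Replace the fragment in Section 6.2.1 with:

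> Primary effectiveness is the proportion of treated patients in the primary analysis population with a negative 6-month mapping biopsy. MRI verification of index lesion ablation is reported separately as a supportive proportion and cannot change the biopsy classification. Treated patients without a 6-month biopsy stay in the denominator and count as not successful, with a sensitivity analysis among biopsied patients.

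In the same text:

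- State whether 'negative' refers to the treatment zone or the whole gland; without that the rule still does not give one number.
- Report how many patients exited as screen failures after the first therapeutic sonications, and show the proportion with and without them.
- Report the proportion by site reading beside the one with central precedence, because central review can move results only towards success.

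The cost is wording and a few extra table rows. Biopsy and MRI are already scheduled for all patients at 6 months, and the site reading exists before any central review. The wording has to be agreed with FDA, since Section 6 ties the efficacy analysis to an FDA agreement. It should be settled before results are summarised: Section 6.1 reports 81 patients already treated under Amendment 4 by 20 September 2018. The downside for the sponsor is that the headline proportion may be lower than under the 'or' reading.
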